Diet and Hypertension Management in African Americans with Chronic Kidney Disease

NCT04084574

Document Date: 12/13/2023

Purpose of the Study

Aim 1. Identify self-perceived barriers and facilitators of DASH diet adherence among African Americans with CKD. We expect self-perceived barriers to DASH diet adherence will include economic concerns, food insecurity, convenience of unhealthy foods, personal and household member food preferences, and cultural norms. We expect the facilitators of DASH diet adherence will include perceived social support and food access.

Aim 2. Evaluate the preliminary impact of diet counseling on DASH diet adherence, 24-hour ambulatory blood pressure, and serum potassium concentration among African Americans with hypertension and CKD. We hypothesize that DASH diet counseling will increase DASH adherence score and reduce 24-hour ambulatory blood pressure without causing hyperkalemia. We hypothesize that DASH diet counseling will reduce office blood pressure without adversely affecting serum phosphorus, calcium, bicarbonate, parathyroid hormone, 25-vitamin D, creatinine, and urine albumin. We hypothesize that diet quality at 3-month follow up will be lower compared to diet quality at week 12 (immediately post-intervention), but higher compared to diet quality at baseline.

Background & Significance

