Study design and population – We will recruit 50 African Americans ≥ 21 years old with a history of hypertension and moderate-to-severe CKD defined as an eGFR of 20-59 ml/min/1.73m². Participants will be randomized in 1:1 fashion to a standard-of-care control arm or an intervention arm.

Study protocol

Control arm: Participants in the control arm will meet individually with the study dietitian for a single 30-minute diet counseling session that will occur face-to-face or via videoconference. They will be advised to limit sodium intake to less than 2.3 grams/day per 2020 National Kidney Foundation's Kidney Disease Outcomes Quality Initiative clinical practice guideline for nutrition in CKD. They will be given educational handouts and tip sheets on how to reduce dietary sodium. Because DASH is not included in current CKD

nutrition guidelines and is not standard-of-care in CKD, participants in the control arm will not be provided with information about the DASH diet. Participants will be permitted to bring one household member/health advocate with them to their counseling session since engagement and social support during nutritional counseling is associated with improved diet adherence.

Intervention arm: Similar to the control arm, participants in the intervention arm will also meet individually with the study dietitian for a single 30-minute counseling session to limit daily sodium intake to less than 2.3 grams/day. However, intervention arm participants will additionally attend 12 weekly dietitian-led group counseling sessions lasting approximately 60-90 minutes. Group counseling will occur in-person and/or via videoconference and will aim to increase participants' adherence to the DASH dietary pattern. Participants will be permitted to bring one household member/health advocate with them to their counseling sessions since engagement and social support during nutritional counseling is associated with improved diet adherence.

All participants will be asked to continue their same anti-hypertensive medications (i.e., no dose changes) and maintain their usual level of physical activity during the 3-month study period. All participants will also have the option to consent to an additional blood sample to be collected, stored and used for future research.

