To evaluate preliminary efficacy of our counseling intervention on DASH adherence, BP, and potassium, we will repeat 24-hour diet recalls, 24-hour urine biomarker studies, office BP, 24-hour ABP, and clinical laboratory studies for all study participants at weeks 12 (post-intervention; primary endpoint) and 24 (after a 3-month post-study observation period; exploratory endpoint). We anticipate that active arm participants will exhibit greater improvement in DASH adherence and a larger reduction in 24-hour mean SBP. Initial summary statistics and graphical displays will be used to make reasonable outcome distribution assumptions. Using an intention to treat, primary analyses to compare the amount of change over time and trajectories of change between the two study arms in DASH diet score, 24-hour mean SBP, and serum potassium will use generalized linear mixed models, with a random effect to capture longitudinal within-person correlation. The primary model for BP outcomes will include study arm, time point, and their interactions, consistent with the randomized trial. Subsequently, a secondary model will be refit to adjust for age, gender, race baseline daily sodium intake, and time-specific values of eGFR, weight, and hypertension medication indicator. Exploratory outcomes in office SBP and DBP, 24-hour DBP, 24-hour urine biomarkers of diet adherence (potassium, phosphorus, urea, and sodium), and additional CKD-relevant metabolic markers (serum phosphorus and bicarbonate) will be assessed using the same analytic strategy. Our analytic approach can be used with any distribution within the exponential family (e.g., normal, binomial, Poisson, and skewed distributions such as gamma and lognormal). The decision on which is most appropriate will be made using initial summary statistics and graphs. The exponential family is broad enough that further transformations of the data are not expected to be necessary, but if so, we will use historically-common transformations to approximate normality. The proportion of participants who do and do not meet safety thresholds (serum potassium >5.2 mg/dl per testing lab standards, phosphorus >5.5 mg/dl, bicarbonate <18 mmol/L) in the two study arms will be compared using the same longitudinal generalized linear mixed model approach, assuming the Binomial distribution.

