Unlike a large clinical trial, our pilot study will not have statistical power to establish the effectiveness and safety of DASH in this population. However, this initial pilot study will generate critical evidence for estimating effect sizes and showing feasibility of the intervention, that will guide future work. Power:

Our power estimate is based on the primary aim comparing treatment arms on the SBP measure. Assuming a 20% attrition rate of 5 per group and using two-sided tests at a type I error rate of 5%, a final sample size of 20 per group will give us 80% power to detect a 7.7 mmHg difference in the change in SBP at 12 weeks between groups, assuming a within-person correlation of 0.7 over time and a standard deviation of SBP of 11 mmHg. A between-group difference of 11.4 and 7.8 mmHg were observed in prior DASH feeding and counseling intervention studies. To assess the sensitivity of the results to any missingness in the data, we will use multiple imputation to create complete cases while incorporating the uncertainty in doing so in the assessment of model parameters. The SAS/STAT software, version 15.1 for Windows and R packages (version 3.6.1) will be used for the data analyses, after extraction from the research database REDCap (Research Electronic Data Capture).

Phase 2c: For this qualitative aim, self-reported barriers and facilitators to DASH diet adherence among active arm participants will be described. Interview transcripts will be analyzed using framework analysis. A thematic analysis approach will be used to allow new concepts to emerge inductively from the data.

Data & Safety Monitoring

Safety monitoring:

Hyperkalemia: Hyperkalemia is the most serious potential risk that CKD patients who follow the DASH diet may experience. Therefore, we plan to actively monitor serum potassium concentrations during the intervention and intensify monitoring during periods that elevations in potassium, if they occur, would most likely be observed. When and how frequently we plan to measure serum potassium has been determined by:

- when participants will be counseled about potassium-rich and potassium-poor foods by the dietitian (i.e., week 2-3);
- knowledge about timing of steady-state concentrations of potassium following increased oral intake; and

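### The secondary blood pressure model adjusts for eGFR, weight and medication measured after randomisation, so its arm-by-time estimate should not be read as a covariate-adjusted treatment effect

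*Combined protocol and SAP*

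**What the plan says.** All of the modelling text is in Data Analysis & Statistical Considerations, Phase 2b analytic strategy.

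- ITT is attached to the primary analyses: "Using an intention to treat, primary analyses to compare the amount of change over time and trajectories of change between the two study arms".
- The primary BP model contains no covariates: "The primary model for BP outcomes will include study arm, time point, and their interactions, consistent with the randomized trial".
- A secondary model is then refit to "adjust for age, gender, race baseline daily sodium intake, and time-specific values of eGFR, weight, and hypertension medication indicator". Sodium intake is specified at baseline; eGFR, weight and medication are specified at each time point.
- The time points are "weeks 12 (post-intervention; primary endpoint) and 24 (after a 3-month post-study observation period; exploratory endpoint".
- Office BP, 24-hour DBP, urine biomarkers and further metabolic markers are exploratory outcomes handled by the same approach.
- The pilot's purpose is stated just before the power paragraph: "this initial pilot study will generate critical evidence for estimating effect sizes and showing feasibility of the intervention, that will guide future work". The model that supplies those effect sizes is not named.

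Two other statements bear on the covariates. Design & Procedures, Aim 2, asks participants to "continue their same anti-hypertensive medications (i.e., no dose changes) and maintain their usual level of physical activity during the 3-month study period". Purpose of the Study, Aim 2, expects counseling to lower office BP "without adversely affecting serum phosphorus, calcium, bicarbonate, parathyroid hormone, 25-vitamin D, creatinine, and urine albumin". The coding of the medication indicator is not given, and nothing says how to read a difference between the two models.

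**The concern.** A covariate measured after randomisation can be part of the response to treatment. Only the intervention arm attends 12 weekly dietitian-led group sessions on the whole dietary pattern, so a weight difference between arms is possible. Creatinine, from which eGFR is normally calculated, is itself an Aim 2 outcome. The request for stable antihypertensive medication covers the 3-month study period and is not extended to week 24.

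Conditioning on such a variable removes the part of the BP effect that runs through it. If the variable reacts to BP, conditioning mixes its own effect on BP into the comparison. Either way, the quantity is no longer the effect of being randomised to counseling. An adjusted estimate printed beside an unadjusted one is easily taken as the same effect with better precision. With two BP estimates and no reading rule, the choice of effect size for a later trial could be made after the results are seen.

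**Working it through.** **1. The plan's own figure.** Inputs from the power paragraph: SD 11 mmHg, within-person correlation 0.7, 20 per group, 7.7 mmHg, two-sided 5%.
- SD of change = 11 x sqrt(2 x (1 - 0.7)) = 8.52 mmHg.
- Standard error of the arm difference = 8.52 x sqrt(2/20) = 2.69 mmHg.
- 7.7/2.69 = 2.86. Power is 81.5% (normal) or 79.5% (t), against 80% stated.
- "Assuming a 20% attrition rate of 5 per group" takes 25 to 20 per group.

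This calculation uses change in SBP without covariates. It matches the primary model and does not involve the secondary one.

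**2. Size of the shift for weight.** The documents give no weight effect, so these inputs are assumptions: arm difference in weight change 1-3 kg (more loss with counseling), within-person slope 0.5-1 mmHg/kg, between-person slope 0-0.8 mmHg/kg, baseline weight SD 10-20 kg, SD of weight change 3 kg. The total effect is set to -7.7 mmHg. A random-intercept model was fitted with and without time-varying weight at two visits, in simulated samples of at least 100,000 per arm.

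With complete data, shift = -(fitted weight coefficient x arm difference in weight change). The fitted coefficient is a compromise between the within- and between-person slopes.

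| Arm difference (kg) | Within slope | Between slope | Weight SD (kg) | Coefficient | Shift toward zero (mmHg) |
|---|---|---|---|---|---|
| 1 | 0.5 | 0 | 20 | 0.02 | 0.02 |
| 3 | 1 | 0 | 10 | 0.13 | 0.40 |
| 3 | 1 | 0.4 | 20 | 0.41 | 1.23 |
| 3 | 1 | 0.4 | 10 | 0.47 | 1.42 |
| 3 | 1 | 0.8 | 10 | 0.81 | 2.43 |
| 0 | 1 | 0.4 | 10 | 0.47 | 0.00 |

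- 1.42/2.69 = 0.53 and 2.43/2.69 = 0.90 standard errors.
- The 0.8 slope is compatible with the plan's variance: between-person SBP variance is 0.7 x 121 = 84.7, and weight would account for 0.8² x 10² = 64 of it.
- If the two slopes are equal, the coefficient is that slope: 0.5 x 1 = 0.50 mmHg and 0.5 x 3 = 1.50 mmHg. The table's top row is therefore not a ceiling.
- With no true arm difference, chance imbalance at 20 per arm still moves single-trial estimates (SD of the shift 0.48 mmHg in one scenario). That is noise, not bias.

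**3. Direction for medication.** Assume a drug is added in response to high BP in 12% of the intervention arm and 32% of controls, the indicator records the addition, and there is no arm difference in weight change.
- Drug effect 8 mmHg: unadjusted -6.11, adjusted -6.82, a shift of 0.71 mmHg away from zero.
- Drug effect 5 mmHg: -6.71 against -6.82, a shift of 0.11 mmHg away from zero.

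The rates, drug effects and coding are all assumed. If the indicator is yes/no use, adding a drug for someone already treated would not change it. No size is offered for eGFR.

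**4. Baseline values instead.**
- With complete data, a main effect of baseline weight leaves the arm-by-time estimate unchanged (difference below 1e-10).
- With 25 per arm and 5 per arm missing week 12 at random (3 kg, 1 mmHg/kg, between-person slope up to 0.4), the baseline-adjusted estimate differs from the unadjusted one by 0.00 on average and 0.04-0.41 mmHg in mean absolute size. The time-varying model still shifts by 0.34-1.37 mmHg on average.

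**The case against.** The strongest reply is that the plan already separates the two models. ITT belongs to the primary analyses, the covariate-free model is primary, and the adjusted model comes afterwards as secondary. A reader might infer that the plan passes off the secondary estimate as an ITT effect, or that the trial's main BP result is biased. Neither inference is supported: the plan never describes the secondary estimate as ITT, and the primary model has no post-randomisation covariates. The problem is a gap in interpretation, not a contradiction.

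Divergence between arms is also not shown. There is no weight or calorie target, Aim 2 expects no adverse effect on creatinine, and the medication request mostly closes that route at week 12, leaving mainly the exploratory week 24. This stands, and it is why the point is conditional.

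Baseline adjustment also largely repeats the primary analysis when data are complete, and multiple imputation is already planned as a sensitivity analysis for missing data. A look at BP at given weight and medication has some descriptive interest. This stands too, and the fix allows for it.

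Finally, the pilot disclaims power to establish effectiveness, and the study was ended while a fifth cohort was in screening, so 20 per arm may not have been reached. The 2.69 mmHg standard error is a planning figure.

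What remains is that the text specifies time-specific values, gives no reading rule and leaves the source of effect sizes unnamed.

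**Conclusion.** The point holds in a limited form. To the extent that counseling or BP moves eGFR, weight or medication, the secondary arm-by-time estimate is an effect with that movement held fixed. If the arms do not diverge on them there is no bias.

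A reader might infer from the weight examples that the distortion is always toward zero, or that it is capped at about half a standard error. The documents support neither. The 0.02 to 2.4 mmHg range rests wholly on assumed weight differences and slopes, its upper end moves with the between-person slope, and the medication example goes the other way.

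The issue may extend to the exploratory outcomes handled by the same approach. It does not reach the primary BP model, power or sample size. Severity: minor, secondary analysis only.

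**What to change.** In the Phase 2b analytic strategy:

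1. In the secondary model, replace the time-specific values with baseline eGFR, weight and antihypertensive medication, alongside age, gender and baseline sodium intake. Drop race: every Aim 2 participant is Black by eligibility, so the term is constant and dropping it changes no estimate.
2. If the time-specific model is still wanted, keep it as a separate analysis labelled exploratory. Define the medication indicator, show eGFR, weight and medication by arm and visit beside the model, and do not present it as an adjusted treatment effect.
3. State that effect sizes for future work come from the primary model.
4. Say whether the secondary model also applies to the exploratory outcomes; if so, apply the same rule there.

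The cost is a few sentences and, under item 2, one descriptive table. Weight, medications and a metabolic panel are listed under Data collection, and clinical laboratory studies are repeated at weeks 12 and 24. The downside is small: with complete data the baseline version returns the primary estimate, so it is useful mainly when visits are missing, and the view of BP at given weight and medication is lost unless item 2 is used. Sample size and power do not change.

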- Stable kidney function

- Videoconference capabilities (access to mobile phone, laptop, desktop or tablet with working camera and internet connectivity)

Exclusion Criteria

- History of kidney transplant
- Receiving chronic dialysis
- Pregnant, lactating, or planning to become pregnant in 9 months
- Risk factors for hyperkalemia
- Screening serum potassium >5.0 mg/dl
- Screening serum bicarbonate <20 mg/dl
- History of hyperkalemia in the preceding 6 months defined as serum potassium greater than 5.0 mg/dl
- Use of oral potassium binders
- Dual therapy with an ACEI and an ARB
- Type 1 diabetes mellitus
- Type 2 diabetes with increased risk for glycemic event
- Hemoglobin A1C >10
- Hospitalization for glycemic event within the preceding 12 months
- If prescribed insulin or insulin secretagogue and unable to obtain permission from diabetes provider to participate in the study
- Change in anti-hypertensive medications within prior 4 weeks
- Hospitalization for hypertensive emergency in the preceding 6 months
- Hospitalization for psychiatric event in preceding 6 months
- Lack of English language proficiency
- Cardiovascular event within the preceding 12 months
- Excess alcohol use (>14 servings/week)
- Active malignancy other than prostate cancer and non-melanomatous skin cancer
- Inability to follow the study diet
- Special dietary requirements or restrictions other than vegetarianism (e.g., vegan)
- Resident of long-term care facility
- Household member of active study participant
- Participating in another clinical trial that will interfere with study activities or confound study outcomes

Subject Recruitment and Compensation

This study will use tools available in Maestro Care, such as DEDUCE (Duke Enterprise Data Unified Content Explorer) and Slicer/Dicer search tools, to help identify and recruit potential participants before consent is signed. We will also screen the schedules of clinics that are attended by our target population in high volume (e.g., nephrology, cardiology, hypertension clinic). Only key personnel who are delegated the task of patient identification/recruitment will have access to this information in Maestro Care. Prospective participants will be referred to the study by the following means:

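### If the binomial mixed model for the safety thresholds includes arm by time with baseline as a response, its change-from-baseline contrast for potassium and bicarbonate is fragile, because entry limits stricter than the event cut-offs can leave baseline cells empty

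*Combined protocol and SAP*

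**What the plan says.** In the combined protocol and SAP, the Phase 2b analytic strategy sets the binary safety cut-offs as "serum potassium >5.2 mg/dl per testing lab standards, phosphorus >5.5 mg/dl, bicarbonate <18 mmol/L" and says that the proportions in the two arms "will be compared using the same longitudinal generalized linear mixed model approach, assuming the Binomial distribution". It describes the approach being reused as "primary analyses to compare the amount of change over time and trajectories of change between the two study arms in DASH diet score"; ambulatory systolic pressure and potassium are the other outcomes named, and a random effect allows for repeated measures on a person. Fixed effects are spelled out once, for another outcome: "The primary model for BP outcomes will include study arm, time point, and their interactions". The same section schedules "clinical laboratory studies for all study participants at weeks 12 (post-intervention; primary endpoint) and 24".

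The Aim 2 exclusion criteria (Selection of Subjects) include "Screening serum potassium >5.0 mg/dl", "Screening serum bicarbonate <20 mg/dl" and "History of hyperkalemia in the preceding 6 months defined as serum potassium greater than 5.0 mg/dl". Phosphorus has no entry limit.

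The section names no method for sparse or zero counts. It allows other exponential-family distributions and transformations, and it plans multiple imputation for missing data. Neither deals with a cell that has no events.

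**The concern.** The two parts of the plan pull against each other. Eligibility removes people whose potassium or bicarbonate is near the event range, and the reused model, on its natural reading, measures each arm's change from that filtered baseline. A log odds needs at least one event and one non-event. Where a baseline cell has no events, the baseline log odds goes to minus infinity and takes the arm-by-time term with it.

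Aim 2 hypothesises lower blood pressure without hyperkalemia, and this is the planned between-arm comparison of hyperkalemia as an event. The section concedes that the pilot has no power to establish safety but says that it should yield effect sizes. Low power gives a wide interval. An unidentified contrast gives no interval, and the analyst would then have to pick a replacement with the event counts by arm already known.

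**Working it through.** **Inputs from the documents.** 50 participants randomised 1:1, so 25 per arm; 20% attrition, so 25 × 0.8 = 20 per arm at week 12. Potassium: entry at 5.0 or below, event above 5.2. Bicarbonate: entry at 20 or above, event below 18.

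**The plan's own figure.** There is none for the threshold analysis. The sample size it rests on reproduces: SD of change = 11 × √(2 × (1 − 0.7)) = 8.52 mmHg, and with 20 per group the t-based power for 7.7 mmHg is 0.795, against the stated 80%.

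**Case 1: the screening draw is week 0.** Nobody at or below 5.0 is above 5.2, and nobody at or above 20 is below 18, so both baseline cells are 0/25. Take week 12 at 4/20 (DASH) and 1/20 (control) as an illustration. In a random-intercept logistic model, the profile negative log-likelihood is 13.978 at every interaction value from −20 to +20 and at every random-intercept SD from 0.5 to 2.5. That equals the value from week 12 alone:

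−[4 ln 0.20 + 16 ln 0.80 + ln 0.05 + 19 ln 0.95] = 13.978.

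The data carry no information on the interaction.

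**Case 2: week 0 is a separate draw.** With baseline 0/25 (DASH) and 1/25 (control), random-intercept SD 0.5, the negative log-likelihood is 18.81, 18.22, 18.19 and 18.19 at interaction values 1.5, 5, 10 and 20. It keeps falling towards plus infinity. With one event in each baseline cell, the lowest grid value is at 1.5, so the estimate is finite. The empty cell is the cause, and the random intercept does not cure it.

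**How often a baseline cell is empty in case 2.** For a baseline event rate p, the chance that at least one arm has none is 1 − [1 − (1 − p)^25]². This gives 98.6%, 95.1%, 84.3% and 47.8% at assumed p of 0.5%, 1%, 2% and 5%.

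A simulation requires an entry draw within the potassium limit, then takes separate week-0 and week-12 draws. All means and SDs are assumptions, because the documents give none. The last two columns run over an assumed DASH effect on potassium of 0 to +0.3.

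| Mean, between-person SD, within-person SD | ≥1 baseline cell empty | ≥1 week-12 cell empty | Any of four empty |
|---|---|---|---|
| 4.4, 0.30, 0.25 | 93% | 83–95% | 98–99% |
| 4.5, 0.35, 0.25 (main) | 79% | 65–85% | 91–96% |
| 4.6, 0.40, 0.30 | 44% | 35–55% | 61–73% |
| 4.8, 0.40, 0.30 | 17% | 15–28% | 29–39% |

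For bicarbonate with both limits read as mmol/L (mean 23, SDs 2.5 and 2.0, no effect), at least one baseline cell is empty in 76%; over means 22 to 24 with SDs 2.0–2.5 and 1.5–2.0 the range is 54% to 99%.

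**Week 12, a separate cause.** Rare events and about 20 per arm can empty these cells whatever the entry limits. The chance that at least one arm has no event is 1 − [1 − (1 − p₁)^20][1 − (1 − p₀)^20]: 79% (5% vs 2%), 71% (10% vs 2%), 44% (10% vs 5%) and 13% (20% vs 10%).

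**The alternative stays finite.** Miettinen-Nurminen 95% intervals for the risk difference: 4/20 vs 1/20 gives 15% (−7% to 38%); 2/20 vs 0/20 gives 10% (−7% to 30%); 0/20 vs 0/20 gives 0% (−16% to 16%).

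**The case against.** The threshold sentence compares proportions between arms and names no change-from-baseline odds ratio. Interaction terms are written out only for blood pressure, and nothing says that baseline is a response row for the binary outcomes. This stands: the failure is conditional on how the plan's reference back to the same approach is read. It is the natural reading, because that approach is described as comparing change over time, but it is an inference.

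A reader might infer that no effect size for hyperkalemia can result. The documents do not support that. The week-12 arm odds ratio is finite when both arms have events. A model with arm and time but no interaction also gives a finite arm effect: log odds ratio 1.40, SE 1.07, in the 4/20 vs 1/20 illustration. Continuous potassium, a primary analysis, does not depend on the cut-off.

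A reader might also infer that failure is near certain. That holds only if screening serves as week 0, which the available text does not say (Table 1 is not shown). Otherwise the rate depends on assumed inputs. The safety-monitoring section describes the target population as CKD stages 3b and 4, so the higher potassium means, where empty cells are less common, cannot be ruled out.

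Finally, software may stop at a large coefficient whose sign opposes the raw proportions (one fit of case 1 gave −27.2, SE 477). That is an arbitrary stopping point on a flat likelihood and does not show a misleading result.

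The admitted lack of power for safety is not an answer, since it concerns precision and not whether the contrast exists.

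**Conclusion.** The point holds as a minor one. If the binomial model carries arm, time and arm by time with baseline as a response, the change-from-baseline odds ratio is not identified for potassium and bicarbonate when screening is week 0. When week 0 is a separate draw, it is infinite or not identified wherever a baseline cell is empty: about 17% to 93% of trials over the assumed potassium inputs, 79% in the main case. Empty week-12 cells add to this but come from rare events and small arms, not from the entry limits.

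The bicarbonate half assumes one unit for both limits. They are printed in mg/dl at entry and mmol/L in the analysis section, and the two passages must be reconciled. The two potassium limits share a printed unit. Phosphorus is outside the claim, having no entry limit.

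**What to change.** Amend the SAP wording for the binary safety outcomes, before exceedances by arm are tabulated:

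1. Do not use the change-from-baseline binomial contrast. Compare exceedance by arm at each scheduled post-baseline visit with labs in both arms: week 12 (main), week 24 (exploratory), and week 4 if Table 1 schedules labs in both arms then. Subject Recruitment and Compensation suggests that it does, since it pays both groups for week-4 assessments and prorates payment for biospecimens at each visit.
2. Give each arm's proportion with a Clopper-Pearson interval and the risk difference with a Miettinen-Nurminen interval. A Firth-penalised logistic model with arm only is optional. Use the same summary for phosphorus.
3. Analyse as randomised and show the number missing per arm. In the planned multiple-imputation sensitivity analysis, impute the continuous lab value and then apply the cut-off, so that it runs even when an arm has no events.
4. Report draws made in only one arm, and reflex draws, descriptively and outside the between-arm comparison. Monitoring itself is unchanged.

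This needs no extra data. The price is that there is no single longitudinal model for exceedances and the intervals are wide, as the 4/20 vs 1/20 example shows. Other sparse-data methods would also serve; what matters is that one is named in advance.
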